8.7.2 Key Secondary Effectiveness Analyses

For the key secondary analysis of effectiveness, the *de jure* estimand will be used to estimate the change from baseline due to MDMA-assisted psychotherapy on PTSD on the SDS in the intended population of patients with PTSD from any cause. The SDS is a 3-item scale measuring the severity of disability in the domains of work, family life/home responsibilities and social/leisure activities. Each of these three domains is scored on a ten-point Likert scale, where a score of 0 is 'not at all impaired', 5 is 'moderately impaired' and 10 is 'very severely impaired'. For each study participant at each visit, the responses on the 3 items of the SDS will be summarized with a mean. In cases where the response on item 1 is not applicable, it will not be considered missing data. Thus, missing data assumptions and methodologies are not required when item 1 is not answered. Whereas when all 3 items have a response, the summary measure is the mean of the 3 item responses, in the cases where item 1 is not answered the summary measure will consist of the mean of items 2 and 3. It is expected that no more than 20% participants will have not have an applicable score for item 1, based on prior studies of paroxetine with PTSD. To limit missing data and ensure standardized administration, the SDS will be administered in a clinician-rated format during the same visits as the CAPS-5 by the centralized Independent Rater Pool.

A secondary estimator of effectiveness will be the mean change in SDS Mean Scores from Baseline to 14 weeks after start of dosing (Visit 14). Least squares means from a restricted maximum likelihood (REML)-based mixed model for repeated measures (MMRM) will be used to estimate the change from baseline to each visit. SDS data collected after treatment discontinuation will not be included in the *de jure* estimand. Missing data will not be imputed and will be considered missing at random.

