## 6.2 Secondary Outcome Measure

#### **Sheehan Disability Scale (SDS)**

The SDS is a clinician-rated assessment of functional impairment [73]. The items indicate degree of impairment in the domains of work/school, social life, and home life, with response options based on an eleven-point scale (0=not at all to 10=extremely), and five verbal tags (not at all, mildly, moderately, markedly, extremely). For participants who are not able to work for reasons related to PTSD, the functional impairment item will be scored as a 10. The SDS takes 1 to 2 minutes to complete [73, 74].

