### 13.1.1.2 Secondary Outcome Analyses

Sheehan Disability Scale (SDS), the secondary outcome measure, will be analyzed in the same manner as the Primary Outcome. The secondary estimator of effectiveness will be the mean change in SDS Mean Item Scores from Baseline to 14 weeks after start of dosing (Visit 14). Least squares means from a REML-based MMRM will be used to estimate the change from Baseline to each visit. SDS data collected after treatment discontinuation will not be included in the de jure estimand.

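### Does the visit-by-visit choice between two and three SDS items distort the change from Baseline enough to need a change to the SAP?

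*SAP*

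**What the plan says.** The SDS is the only secondary outcome. Protocol 13.1.1.2 defines its estimator as the "mean change in SDS Mean Item Scores from Baseline to 14 weeks after start of dosing", taken from a mixed model for repeated measures. SAP 8.7.2 gives the scoring: "For each study participant at each visit, the responses on the 3 items of the SDS will be summarized with a mean". It then makes one exception: "In cases where the response on item 1 is not applicable, it will not be considered missing data", and "in the cases where item 1 is not answered the summary measure will consist of the mean of items 2 and 3". It adds a forecast: "It is expected that no more than 20% participants will have not have an applicable score for item 1".

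Two sentences in Protocol 6.2 bear on the exception. One names the domains: "The items indicate degree of impairment in the domains of work/school, social life, and home life". The other fixes the score for the most relevant group: "For participants who are not able to work for reasons related to PTSD, the functional impairment item will be scored as a 10". SAP 8.7.2 does not repeat the second sentence, and it lists the domains as "severity of disability in the domains of work, family life/home responsibilities and social/leisure activities", without mentioning school.

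**The concern.** The endpoint is a within-person change, but the score at each end of that change may rest on different items. Someone with three items at Baseline and two at Visit 14 can show a change when items 2 and 3 have not moved at all. The study has one arm, so no comparison group would show the same shift. The supportive *de facto* analysis in SAP 8.2 covers CAPS-5 only, so no sensitivity analysis is named for the SDS.

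The wording adds to the doubt. The text moves from *not applicable* to *not answered*. Read literally, an applicable item that was simply skipped would be rescored on two items and never counted as missing. The SAP also leaves out the score-of-10 rule. A participant at 10, 6, 6 scores 22/3 = 7.33 under Protocol 6.2, but 6.00 if item 1 is left blank. What would be at stake is a spurious part of the mean SDS change, in either direction.

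**Working it through.** **Inputs.** Items run from 0 to 10 (Protocol 6.2). Up to 40 participants (Protocol 4.1). Visit 14 falls 67 to 112 days after Visit 3 (Protocol Table 1). Up to 20% have no applicable item 1 (SAP 8.7.2), which is 8 of 40. The SAP states no figure for the effect of the rule, so there is none to reproduce.

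**One person.** Write x1, x2, x3 for the items and m = (x2 + x3)/2. Then

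(x1 + x2 + x3)/3 − m = (x1 − m)/3.

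Compared with using items 2 and 3 throughout, a switch of applicability moves the change by one third of the gap x1 − m:

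- gap 0: 0
- gap 2: 0.67
- gap 4: 1.33
- gap 10 (the largest possible): 3.33

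So the effect on one person's change need not be small.

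**The group mean.** Shift = (net switchers / 40) × gap / 3. The numbers of switchers and the gaps are assumed.

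| Net switchers | Gap 2 | Gap 4 |
|---|---|---|
| 2 of 40 | 0.033 | 0.067 |
| 4 of 40 | 0.067 | 0.133 |
| 8 of 40 | 0.133 | 0.267 |

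The last row takes the SAP's 20% as an extreme: nobody without item 1 at Baseline, and 8 without it at Visit 14. With the largest gap it would give 8/40 × 10/3 = 0.67. That reading is strained. The 20% is a share without an applicable item, not a share who change. If the share were 20% at every visit, as many people would enter that state as leave it. Net switchers would be zero, and the shifts would cancel when the average gap is the same in both directions.

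**The likeliest route.** Take a participant who cannot work because of PTSD at Baseline and later returns to work. Under Protocol 6.2 the items might go from 10, 6, 6 to 4, 6, 6, so the scores go from 7.33 to 16/3 = 5.33. Both rest on three items, and the change of −2.00 is real. The same holds for someone who stops working because of PTSD. A switch needs a change in work or school status for some other reason within 67 to 112 days.

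**What planned output would show.** SAP 8.7 gives descriptive statistics with n for all endpoints and plots the SDS items by visit. Protocol Table 4 lists change in SDS item scores from Visit 3 to Visit 14. SAP 8.0 provides data listings. Among participants assessed at both visits, let a and b be the numbers with item 1 at Visit 3 and Visit 14, and c the number with a paired item 1 change. Then a − c lost the item, b − c gained it, and a + b − 2c switched. Averaging the mean changes of items 2 and 3 gives a two-item result for everyone, as a descriptive check.

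**What a constant-item model would add.** Let items 2 and 3 stay at 6, with item 1 at 10, then 4, then not applicable at Visits 3, 8 and 14.

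| | V3 | V8 | V14 | Change V8 | Change V14 |
|---|---|---|---|---|---|
| SAP rule | 7.33 | 5.33 | 6.00 | −2.00 | −1.33 |
| Items 2 and 3 only | 6.00 | 6.00 | 6.00 | 0 | 0 |

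The SAP rule gives an apparent worsening of 0.67 from Visit 8 to Visit 14, which is an artefact. The constant set removes it, but it also erases the real drop from 10 to 4 at Visit 8, where all three items were present. A difference between the two models would mix the artefact with true change in item 1.

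**The case for a change.** The best case for a change is that it costs a few sentences and one model run, needs no new data, and protects the only secondary endpoint in a study with no control arm. A prespecified check also carries more weight than a post-hoc one. Net counts in item summaries can hide switches in opposite directions, and the loose wording could let a skipped item pass as not applicable.

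The facts behind this stand: the item set is not fixed within a person, the identity is right, and one person's change can move by more than a point. The inference is weaker. The paired n and the listings separate switches in the two directions, provided the SDS items are listed. The *not answered* clause follows as a consequence of the sentence on *not applicable* responses, so in context both describe the same cases. The SDS is administered by independent raters, partly to limit missing answers, and Protocol 6.2 governs how the item is scored. *Work* is ordinary shorthand for the protocol's work/school domain. Using the protocol's terms would be tidier, but an analyst with both documents would not score differently. The extra model is itself debatable, because it discards real improvement in work impairment for anyone who switches.

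**Conclusion.** No change follows. The SAP states an explicit, prespecified way to score an item that does not apply to everyone, and any alternative has its own cost. The likely effect on the mean SDS change is about 0.03 to 0.13 points on a 0 to 10 scale. That assumes a net 2 to 4 of 40 switching one way with gaps of 2 to 4, and it is zero if nobody switches or item 1 equals the mean of the other two. The documents supply neither the switching rate nor the gap, so these figures illustrate the size and do not bound it. The far extreme of 0.67 needs 8 people all switching one way with the largest possible gap. The study has no power calculation (SAP 7.0), and the documents set no SDS threshold that a shift of this size could cross. The differences in wording between SAP 8.7.2 and Protocol 6.2 are clerical and resolve when the two are read together.

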8.7.3 Exploratory Analyses

[figure not shown]
Post-hoc exploratory analyses not identified in this SAP may be performed to further examine the study data. These analyses will be clearly identified as such in the final clinical study report or in the clinical study report addendum.

In exploratory analyses, additional baseline covariates (age, gender, ethnicity, index trauma, complexity and severity of trauma, medication tapering, diagnosis of comorbid depression, diagnosis of comorbid Axis 2 diagnosis, adverse childhood experiences) may be assessed for inclusion in the model at a p<0.05. One-group pretest-posttest Cohen's *d* effect size will be estimated.

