## Psychiatric History

- 7. Have received Electroconvulsive Therapy (ECT) within 12 weeks of enrollment.
- 8. Have a history of, or a current primary psychotic disorder, bipolar affective disorder type 1 assessed via MINI and clinical interview or dissociative identity disorder assessed via DDIS and clinical interview.
- 9. Have a current eating disorder with active purging assessed via MINI and clinical interview.
- 10. Have current major depressive disorder with psychotic features assessed via MINI.
- 11. Have a current alcohol or substance use disorder other than caffeine or nicotine that the investigators, therapy team, and/or Medical Monitor judge to be a safety concern for enrollment in the study or that could interfere with the therapeutic process or with other aspects of study participation. Any participant who is not able to agree or adhere to a plan to reduce use and manage symptoms will not be enrolled.
- 12. Have current Personality Disorders (paranoid, schizoid, schizotypal, antisocial, borderline, histrionic, narcissistic, avoidant, dependent, obsessive-compulsive) assessed via CIPD. Diagnoses will be confirmed via clinical interview.
- 13. Any participant presenting current serious suicide risk, as determined through psychiatric interview, responses to C-SSRS, and clinical judgment of the investigator will be excluded; however, history of suicide attempts is not an exclusion. Any participant who is likely to require hospitalization related to suicidal ideation and behavior, in the judgment of the investigator, will not be enrolled. Any participant presenting with the following on the Baseline C-SSRS will be excluded:
  - Suicidal ideation score of 4 or greater within the last month of the assessment at a frequency of once a week or more.
  - Suicidal ideation score of 5 within the last 6 months of the assessment.

- Any suicidal behavior, including suicide attempts or preparatory acts, within the last 6 months of the assessment. Participants with non-suicidal self-injurious behavior may be included if approved by the Medical Monitor.
- 14. Would present a serious risk to others as established through clinical interview and contact with treating psychiatrist.
- 15. Require ongoing concomitant therapy with a psychiatric medication with exceptions described in Section 11.0: Concomitant Medications.

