## 4.0 Protocol Design

#### 4.1 Study Design Overview

This multi-site, open-label study assesses the safety and effectiveness of MDMA-assisted psychotherapy in participants diagnosed with at least severe PTSD. This study will also serve as an experiential training opportunity for therapy teams who will be participating in the upcoming Phase 3 study. The sponsor will provide clinical supervision through the adherence raters and the therapy pair supervisors, who will review the therapy session videos to ensure adherence to the therapeutic method, consistency between sites and therapy pairs, and provide support and advice to the therapy pair.

The study will be conducted in up to 40 participants in multiple countries in Europe. Some sites will participate in the imaging sub-study (see Appendix A for additional details). This study will be conducted in compliance with the protocol, GCP and applicable regulatory requirement(s). All data will be included in the sponsor's safety database.

For each participant, the study will consist of:

- Screening Period: phone screen, informed consent, eligibility assessment, and enrollment of eligible participants
- Preparatory Period with Enrollment Confirmation: medication tapering, Preparatory Sessions and Baseline assessments leading to Enrollment Confirmation
- Treatment Period: two Experimental Sessions spaced a month apart and associated Integrative Sessions over ~8 weeks plus one CAPS-5 assessment
- Follow-up Period and Study Termination: ~4 weeks with no study visits, followed by Primary Outcome CAPS-5 and Study Termination visit

The treatment consists of a flexible dose of MDMA, followed by a supplemental half-dose unless tolerability issues emerge with the first dose or the participant declines, administered with manualized psychotherapy in two open-label Experimental Sessions spaced a month apart. This ~8-week Treatment Period is preceded by three Preparatory Sessions. During the Treatment Period, each Experimental Session is followed by three Integrative Sessions of non-drug psychotherapy. Experimental Sessions are followed by an overnight stay. Study design overview is shown in Table 1 and Figure 1.

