### 13.1.1.3 Exploratory Analyses

One-group pretest-posttest Cohen's *d* effect size will be estimated. Exploratory sub-group analyses may be conducted when possible to evaluate effects and by individual demographic

characteristics (*e.g.*, age, gender, ethnicity, index trauma, ACE score, presence of secondary traumatic stressors during the assessment period with LEC-5, medication tapering, diagnosis of comorbid depression, diagnosis of comorbid diagnosis, and number of experimental sessions completed). Post-hoc exploratory analyses not described in the protocol or Statistical Analysis Plan may be performed to further examine the study data. These analyses will be clearly identified as such in the final clinical study report.

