1.0 Definitions of Terms

Categorical data: refers to discrete (indivisible) variables, such as gender or ethnicity; data will be presented as total numbers of each category as needed to describe the sample

Completers: are defined as participants who complete all two planned experimental sessions and the CAPS-5 outcome assessment 14 weeks after enrollment (Visit 14).

Descriptive data: includes mean, median, standard deviation, minimum, and maximum of numerical data used as needed to describe the sample

Difference scores: consist of scores computed by subtracting one value from another, as subtracting Baseline from follow-up score, used to test for differences between and within groups to determine change as a function of experimental treatment over time

Dropouts: are defined as participants who withdraw consent due to any reason after dosing and no longer participate in the study, i.e. no further contact with investigators or site staff.

Effectiveness: type of analysis used to assess therapeutic effects or benefits

Exploratory analyses: inferential or descriptive analysis of the data to determine trends that might lead to hypotheses for further study

Frequency listing: tabular listing of numbers and/or percentages of events used as needed to describe the sample or data characteristics

Outcome measures: primary and secondary study measures that are used to test the study hypotheses

Post-dosing Early Terminators: are defined as participants who discontinue study treatment but continue to participate in study evaluations and outcome assessments.

Pre-dosing Early Terminators: are defined as participants who discontinue participation after enrollment but before randomization during the Preparatory Period and never receive study drug.

Process measures: study measures or qualitative observations collected during the study that may increase depth of understanding of the condition and treatment, although not necessarily related to safety or effectiveness

Protocol deviation: event that represents significant divergence from the intended study design as described in the protocol

Safety: assessment of indicators of potential risks and adverse events

Safety measures: study measures that assess safety of the Investigational Product (IP), such as heart rate monitoring, blood pressure, body temperature

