8.0 Analyses

Every effort will be made to ensure complete, accurate and timely data collection and to avoid missing data, to ensure the completeness of the data which can impact the integrity and accuracy of the final study analysis. The statistical analyses will be reported using summary tables, figures, and data listings. All analyses and tabulations will be performed using SAS® Version 9.4 or higher, and S-PLUS. In general, nominal variables will be described in terms of frequencies and percentages. Ordinal and non-normal continuous variables will be described using sample median and range.

Approximately normal variables will be described using sample mean and standard deviations and analyzed by parametric statistical tests. Except for the primary effectiveness analysis, all statistical tests will be two-sided and a difference resulting in a p-value of less than or equal to 0.05 will be considered statistically significant. All p-values will be rounded to and displayed in four decimals. If a p-value less than 0.0001 occurs it will be shown in tables as <0.0001. Data not subject to analysis according to this plan will not appear in any tables or graphs, but will be included in the data listings. Selected results may be presented graphically using standard graphical software.

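### The SAP's optional p<0.05 filter on nine baseline covariates, in at most 40 participants, answers the exploratory predictor questions poorly: weak associations that pass are overstated, moderate ones are often missed, and one candidate barely varies

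*SAP*

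**What the plan says.** SAP 8.7.3 begins the relevant sentence with "In exploratory analyses, additional baseline covariates" and lists nine candidates: "age, gender, ethnicity, index trauma, complexity and severity of trauma, medication tapering, diagnosis of comorbid depression, diagnosis of comorbid Axis 2 diagnosis, adverse childhood experiences". These "may be assessed for inclusion in the model at a p<0.05". The text gives no order of entry, does not choose between one-at-a-time and joint testing, applies no multiplicity adjustment or shrinkage, and does not say what is reported for a candidate that fails.

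The surrounding provisions are:

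- SAP 8.0: "Except for the primary effectiveness analysis, all statistical tests will be two-sided", with 0.05 as the significance level.
- SAP 1.0 defines exploratory analyses as "inferential or descriptive analysis of the data to determine trends that might lead to hypotheses for further study".
- Protocol 4.1: "The study will be conducted in up to 40 participants in multiple countries in Europe". SAP 7.0 gives no sample-size calculation, and SAP 8.2 expects early termination in up to 5%.
- SAP 8.7.1 names no covariates in the primary MMRM.
- Protocol Table 4 lists the effect of adverse childhood experiences (ACE) on CAPS-5, treated as a covariate, with no p-value condition. Protocol 13.1.1.3 allows subgroup work: "Exploratory sub-group analyses may be conducted when possible to evaluate effects and by individual demographic" characteristics, ACE score among them.
- Protocol 3.2, exclusion 12, bars people who "Have current Personality Disorders (paranoid, schizoid, schizotypal, antisocial, borderline, histrionic, narcissistic, avoidant, dependent, obsessive-compulsive) assessed via CIPD".

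**The concern.** A significance threshold used as an entry rule does two jobs badly in a sample this small. With nine candidates, it is quite likely to admit something by chance. It also admits only associations that look large in this sample, so whatever is admitted tends to be overstated, while a moderate real association is often left out.

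What is at stake is the reading of the exploratory predictor questions, not the treatment estimate. ACE is the clearest case. The protocol asks for its effect on CAPS-5, but under an entry rule the SAP does not guarantee that any estimate appears. One candidate, Axis 2 diagnosis, also conflicts with the eligibility criteria.

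**Working it through.** The documents state no error rate for this step, so there is no figure of theirs to reproduce.

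**Inputs.** Nine candidates and a threshold of 0.05 (SAP 8.7.3); two-sided tests (SAP 8.0); n at most 40 (Protocol 4.1). With 5% early termination (SAP 8.2), 40 − 0.05 × 40 = 38. *Assumptions not in the documents:* correlation among covariates from 0 to 0.7, and true covariate–outcome correlation r from 0 to 0.5. Ordinary regression or simple correlation stands in for the MMRM.

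**1. Chance that at least one null candidate enters.** Under independence this is 1 − 0.95^k.

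- k = 9: 1 − 0.95^9 = 0.370; expected false entries 9 × 0.05 = 0.45.
- k = 8 (Axis 2 unusable): 1 − 0.95^8 = 0.337.
- k = 10 (complexity and severity of trauma scored separately): 1 − 0.95^10 = 0.401.

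Simulation with nine null covariates, n = 40 and 6,000 runs per setting:

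| Correlation among covariates | Tested one at a time | Tested jointly |
|---|---|---|
| 0 | 0.37 | 0.33 |
| 0.3 | 0.33 | 0.33 |
| 0.5 | 0.27 | 0.33 |
| 0.7 | 0.21 | 0.32 |

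The overall range is about 21% to 40%.

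**2. Size needed to pass.** The critical |r| is t / √(n − 2 + t²), where t is the 97.5% point on n − 2 degrees of freedom. This gives 0.312 at n = 40 and 0.320 at n = 38. A continuous covariate that passes therefore appears to explain about 10% of the variance or more (0.312² = 0.097; 0.320² = 0.10).

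**3. What passing does to the estimate.** Simulation of one covariate, kept only if two-sided p<0.05, n = 40, 200,000 runs per setting:

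| True r | Chance of entry | Mean size when kept, relative to truth |
|---|---|---|
| 0.1 | 9% | 3.8 times |
| 0.2 | 24% | 2.0 times |
| 0.3 | 48% | 1.4 times |
| 0.4 | 74% | 1.16 times |
| 0.5 | 92% | 1.04 times |

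A pure-noise covariate that passes shows a mean |r| of about 0.37. At r = 0.3 the chance of missing it is 100% − 48% = 52%. Results at n = 38 are close: 3.9, 2.0 and 1.4 times at r = 0.1, 0.2 and 0.3.

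**4. Axis 2 against eligibility.** Exclusion 12 names ten personality disorders and covers current diagnoses. Protocol 7.1.4 does not let the investigator overrule a diagnosis that a measure or interview shows. If the SAP means current diagnosis, almost every participant has the same value and no useful coefficient can be estimated.

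**The case against.** The strongest reply is that this is one permissive sentence about exploratory work. The SAP says the covariates may be assessed, not that they will be, and its own definition already treats exploratory results as hypothesis-generating. With no control arm and no covariates named in the primary MMRM, no treatment contrast or primary estimate changes. All of that stands.

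The 37% is also the value for independent candidates that are all null. ACE, trauma severity and depression are plausibly correlated, which lowers the figure if candidates are tested singly. Inflation is an average effect and small for strong predictors. The |r| cut-offs come from simple correlation, not from the planned model. These limits stand too, and are why a range is given. A near-constant Axis 2 variable adds little to false selection, so eight candidates and 34% may be the fairer count.

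Three stronger readings are tempting, and the documents do not support them:

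- *Covariates that fail will go unreported.* The SAP does not say so. It only makes no commitment to report them.
- *This step is the trial's only answer on ACE.* Protocol Table 4 treats ACE as a covariate without a threshold, and Protocol 13.1.1.3 allows ACE subgroups.
- *A chance predictor will become a Phase 3 covariate or stratification factor.* The documents link this study to Phase 3 through power assumptions, reproducibility and training. They say nothing about choosing covariates from it.

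Finally, reporting every estimate with an unadjusted 95% CI leaves about the same chance that some interval excludes zero. That is correct. The gain is the removal of selection and of the inflation it causes.

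**Conclusion.** The point holds as a cheap improvement to an exploratory analysis. If the rule is used and no candidate has an effect, there is about a one-in-three chance of keeping at least one (37% under independence; about 21% to 40% across the settings examined). Weak associations that pass would read about 2 to 4 times too large on average. A true r of 0.3 would fail to enter about half the time, and strong associations would be little distorted. These figures rest on n of about 40, on ordinary regression or simple correlation in place of the MMRM, and on assumed correlations. The Axis 2 conflict needs none of these assumptions, only that the SAP means current diagnosis. The primary and secondary estimates are not in question.

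**What to change.** In SAP 8.7.3, replace the entry rule with a fixed table:

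- Fit each listed covariate in its own MMRM alongside baseline CAPS-5. SAP 8.7.1 does not name baseline as a covariate, so this is an addition. The reason is that change is measured from baseline, so a covariate related to baseline severity could otherwise look predictive for that reason alone.
- Report every estimate with a 95% CI, whatever its p-value, and label the table hypothesis-generating.
- State under the table that about nine unadjusted intervals carry roughly a one-in-three chance that at least one excludes zero by chance (37% for nine, 34% for eight, if independent and null).
- Drop current Axis 2 diagnosis. If a past diagnosis is meant, say so.

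A stricter threshold is not a substitute. Using 0.05 / 9 = 0.0056 would hold the chance of any false entry to about 5%, but it would miss more real associations and inflate the weak ones that pass even further.

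The cost is one SAP sentence and one table, with no new data and no change to the primary analysis. The loss is that no single selected adjusted model is produced. The gain is that the ACE question gets an estimate and an interval whichever way it falls.
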